10.3.5.1.2 Unsolicited AE Intensity Grading Scale

For measurable unsolicited AEs that are part of the list of solicited reactions, the corresponding scale for solicited reactions will be used (see [Section 10.3.5.1.1](#)).

All other unsolicited AEs will be classified according to the following intensity scale:

- Grade 1
 - CRF: A type of adverse event that is usually transient and may require only minimal treatment or therapeutic intervention. The event does not generally interfere with usual activities of daily living.
 - Diary card: No interference with usual activities.
- Grade 2
 - CRF: A type of adverse event that is usually alleviated with additional therapeutic intervention. The event interferes with usual activities of daily living, causing discomfort but poses no significant or permanent risk of harm to the research participant.
 - Diary card: Some interference with usual activities.
- Grade 3
 - CRF: A type of adverse event that interrupts usual activities of daily living, or significantly affects clinical status, or may require intensive therapeutic intervention.
 - Diary card: Significant; prevents usual activities.

10.3.5.2 Tables for Laboratory Abnormalities

The pre-defined intensity thresholds for laboratories abnormalities are shown in [Table 10.4](#).

Table 10.4: Intensity thresholds for laboratories abnormalities

Endpoint	Mild (Grade 1)	Moderate (Grade 2)	Severe (Grade 3)
Hemoglobin (Female) – gm/dL	11.0 – 12.0	9.5 – 10.9	≤ 9.4
Hemoglobin (Female) (Change from baseline value) – gm/dL	Any decrease – 1.5	1.6 – 2.0	≥ 2.1
Hemoglobin (Male) – gm/dL	12.5 – 13.5	10.5 – 12.4	≤ 10.5
Hemoglobin (Male) (Change from baseline value) – gm/dL	Any decrease – 1.5	1.6 – 2.0	≥ 2.1
Above normal WBC – cell/mm³	10,800 – 15,000	15,001 – 20,000	≥ 20,001
Below normal WBC – cell/mm³	2,500 – 3,500	1,500 – 2,499	≤ 1,499
Absolute Lymphocytes Decreased – cell/mm³	750 – 1,000	500 – 749	< 499
Absolute Neutrophils Decreased – cell/mm³	1,500 – 2,000	1,000 – 1,499	< 999
Absolute Eosinophils – cell/mm³	650 – 1500	1501 - 5000	> 5000
Platelets Decreased – cell/mm³	125,000 – 140,000	100,000 – 124,000	≤ 99,000
Creatinine – mg/dL	1.5 – 1.7	1.8 – 2.0	≥ 2.1 or requires dialysis
Blood Urea Nitrogen (BUN) – mg/dL	23 – 26	27 – 31	> 31 or require dialysis
Sodium – Hyponatremia – mEq/L	132 – 134	130 – 131	< 130
Sodium – Hypernatremia – mEq/L	144 – 145	146 – 147	> 148
Potassium – Hyperkalemia – mEq/L	5.1 – 5.2	5.3 – 5.4	> 5.4
Potassium – Hypokalemia – mEq/L	3.5 – 3.6	3.3 – 3.4	< 3.3
Glucose – Hyperglycemia (fasting) – mg/dL	100 - 110	111 - 125	> 125
Total Protein – Hypoproteinemia – g/dL	5.5 – 6.0	5.0 – 5.4	< 5.0
Alkaline phosphate (Increase by factor)	1.1 – 2.0 x ULN	2.1 – 3.0 x ULN	≥ 3.1 ULN
LFT (ALT, AST) (Increase by factor)	1.1 – 2.5 x ULN	2.6 – 5.0 x ULN	≥ 5.1 ULN
Bilirubin – with any increase in LFT (Increase by factor)	1.1 – 1.25 x ULN	1.26 – 1.5 x ULN	≥ 1.51 ULN

Endpoint	Mild (Grade 1)	Moderate (Grade 2)	Severe (Grade 3)
Bilirubin – with normal LFT (Increase by factor)	1.1 – 1.5 x ULN	1.6 – 2.0 x ULN	≥ 2.1 ULN
Pancreatic enzymes – amylase, lipase	1.1 – 1.5 x ULN	1.6 – 2.0 x ULN	≥ 2.1 ULN
Urine - protein	Trace	1+	2+
Urine - glucose	Trace	1+	2+
Urine – blood (microscopic) - RBCs per high power field (rbc/hpf)	1 - 10	11 - 50	> 50 and/or gross blood

Abbreviations: ALT, alanine aminotransferase; AST, aspartate aminotransferase; CPK, creatine phosphokinase; CRP, C-reactive protein; dL, deciliter; gm, gram; LFT, liver function test; mg, milligram; mm³, cubic millimeter; RBC, red blood cell; ULN, upper limit of normal; WBC, white blood cell

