10.2 Appendix: Clinical Laboratory Tests

A urine human chorionic gonadotropin (hCG) pregnancy test (as needed for women of childbearing potential) will be performed before each vaccination.

- The tests detailed in [Table 10.1](#) will be performed by the site-selected local laboratory.
- Protocol-specific requirements for inclusion or exclusion of participants are detailed in [Section 5](#) of the protocol.
- Additional tests may be performed at any time during the study as determined necessary by the Investigator or required by local regulations.
- Pregnancy Testing

Table 10.1: Protocol-required safety laboratory assessments

Laboratory Assessments	Time period for assessment	Parameters			
Hematology	Cohort 1: D01 and V02 (D09) Cohort 2: D01 and V03 (D30)	Platelet Count	White blood cell (WBC) count with Differential: Neutrophils Lymphocytes Monocytes Eosinophils Basophils		
		Hemoglobin			
		Hematocrit			
Clinical Chemistry	Cohort 1: D01 and V02 (D09) Cohort 2: D01 and V03 (D30)	Blood urea nitrogen (BUN)	Potassium	Aspartate Aminotransferase (AST)/ Serum Glutamic-Oxaloacetic Transaminase (SGOT)	Total and direct bilirubin
		Creatinine	Sodium	Alanine Aminotransferase (ALT)/ Serum Glutamic-Pyruvic Transaminase (SGPT)	Total Protein
		Glucose (nonfasting)		Alkaline phosphatase	
		Lipase			
		Amylase			
Routine Urinalysis	Cohort 1: D01 and V02 (D09) Cohort 2: D01 and V03 (D30)	
 Glucose, protein, blood, leukocyte esterase by dipstick Microscopic examination (if blood or protein is abnormal) 			
Other Screening Tests	Cohort 1: pre-injection 1 at D01 Cohort 2: pre-injections 1 and 2 at D01 and V02 (D22), respectively	Highly sensitive urine human chorionic gonadotropin (hCG) pregnancy test (as needed for women of childbearing potential*)			
	D01	Rapid diagnostic testing for SARS-CoV2 antibody screening			

* To be considered of non-childbearing potential, a female must be post-menopausal for at least 1 year or surgically sterile.

Investigators must document their review of each laboratory safety report.

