4.4.1.3 Laboratory test Results

Biological safety tests (biochemistry and hematology) will be performed at local laboratory. Biological endpoints will be assessed on samples taken at screening, V01, V02 (Cohort 1), V03 (Cohort 2), and unscheduled visits based on investigator's judgment, in cases of abnormal safety laboratory results.

The parameters to be evaluated will include serum chemistries (blood urea nitrogen (BUN), potassium, Aspartate Aminotransferase (AST)/serum glutamic-oxaloacetic transaminase (SGOT), total and direct bilirubin, creatinine, sodium, alanine aminotransferase (ALT)/ serum glutamic-pyruvic transaminase (SGPT), total protein, glucose (nonfasting), alkaline phosphatase, lipase, amylase; hematology (platelet count, hemoglobin, hematocrit, white blood cell (WBC) count with differential, neutrophils, lymphocytes, monocytes, eosinophils, basophils); and Urinalysis (Specific gravity, pH, glucose, protein, blood, ketones, bilirubin, urobilinogen, nitrite, leukocyte esterase by dipstick, microscopic examination). The microscopic examination will be done if blood or protein is abnormal.

Endpoints will be defined as either within or outside normal range. Normal ranges for each endpoint will be provided by the study center. The biological safety information will be entered by the site staff in the appropriate CRF forms along with units and normal ranges. In case of out-of-range values, specific endpoints may be rechecked and additional biological parameters may be evaluated, based on the Investigator's judgement. This complementary safety information will also be entered by the site staff in the appropriate CRF forms along with units and normal ranges.

Any change in the testing equipment using different ranges should be reported on an ongoing basis to the Sponsor so that any value can be interpreted at a given time against the appropriate range of values.

Biological safety endpoints will be assessed on whether or not they reach the pre-defined intensity levels (Grade 1, 2, or 3) for analytes with applicable toxicity grading, as specified in the protocol. Table 10.4 of the protocol contains the pre-defined intensity scales according to which the biological safety parameters will be assessed. If at least one of these intensity levels is reached, the Investigator will evaluate the clinical significance of the results and report clinically significant abnormal values as AEs in the CRF.

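### Glucose is drawn nonfasting but Protocol Table 10.4 grades it only on a fasting scale, and other bands give some values two grades or none, so these toxicity grades are misapplied or undefined

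*Protocol*

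**What the plan says.** Protocol Table 10.1 (section 10.2) lists glucose as nonfasting, taken at D01 and again at D09 in Cohort 1 or D30 in Cohort 2. SAP 4.4.1.3 repeats this in its list of chemistries: "glucose (nonfasting), alkaline phosphatase, lipase, amylase".

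Protocol Table 10.4 (section 10.3.5.2) has one serum glucose row, "Glucose – Hyperglycemia (fasting) – mg/dL", with Grade 1 at 100–110, Grade 2 at 111–125 and Grade 3 above 125.

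SAP 4.4.1.3 makes that table the grading scale: "Table 10.4 of the protocol contains the pre-defined intensity scales according to which the biological safety parameters will be assessed". It limits grading to analytes for which a toxicity scale applies. It also says that reaching any grade leads the Investigator to judge clinical significance and report significant values as AEs. SAP 5.1.1.2 then tabulates toxicity grade by visit and grade shift from baseline.

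The primary laboratory endpoint is separate. It is a result outside the normal range supplied by the study center (Protocol Table 3.1; SAP 4.4.1.3).

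**The concern.** A grading scale has to fit the sample it grades and give each value one grade. The glucose row fails the first test, because it is defined for a condition under which no sample is planned. Several other rows fail the second.

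Without a stated rule, the programmer has to invent one. For glucose, the choice is between grading after-meal values on the fasting row and not grading them at all, and the two choices give different tables. If the fasting row is used, the time since the last meal enters both the baseline grade and the post-vaccination grade, so part of any shift reflects when the participant ate. At the faulty boundaries, the grade depends on the order of statements in the code, or is missing.

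**Working it through.** The plan states no figure to reproduce. The check has two parts.

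**Glucose.** Three places were set side by side.
- Protocol Table 10.1: nonfasting.
- SAP 4.4.1.3: nonfasting.
- Protocol Table 10.4: fasting row only.

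Nothing in either document requires fasting, gives a nonfasting scale, or says how nonfasting values are handled. The three glucose bands are contiguous (110 then 111; 125 then above 125), so the fault lies only in the fasting label. The scale is narrow: the highest ungraded whole number is 99 and the lowest Grade 3 value is 126, a difference of 126 − 99 = 27 mg/dL.

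**Other rows.** Each numeric band was tested on a grid at its printed resolution, counting how many grades each value satisfies. One is correct, zero is a gap and two is an overlap.

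| Row in Table 10.4 | Grade 1 | Grade 2 | Grade 3 | Result |
|---|---|---|---|---|
| "Hemoglobin (Male) – gm/dL" | 12.5–13.5 | 10.5–12.4 | ≤ 10.5 | 10.5 has two grades |
| "Sodium – Hypernatremia – mEq/L" | 144–145 | 146–147 | > 148 | 148 has none |
| "Absolute Lymphocytes Decreased – cell/mm³" | 750–1,000 | 500–749 | < 499 | 499 has none |
| "Absolute Neutrophils Decreased – cell/mm³" | 1,500–2,000 | 1,000–1,499 | < 999 | 999 has none |
| Platelets, per mm³ | 125,000–140,000 | 100,000–124,000 | ≤ 99,000 | 99,001–99,999 and 124,001–124,999 have none |

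The platelet gaps hold 999 + 999 = 1,998 whole-number values, but none if the laboratory reports in whole thousands. Creatinine and most rows expressed as multiples of the upper limit of normal have gaps only if more decimals are reported than the table prints (for example, creatinine 1.71–1.79). At printed resolution there is no gap or overlap for female hemoglobin, hemoglobin change, both white-cell rows, eosinophils, BUN, low sodium, both potassium rows, total protein or urine red cells.

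**Where the grades go.**
- *Grade-by-visit and shift tables (SAP 5.1.1.2).* No clinical filter applies, so a misapplied or missing grade passes straight through.
- *Grade-triggered review (SAP 4.4.1.3).* If the fasting row is used, any value of 100 mg/dL or more is sent to the Investigator. A sodium of 148 is not sent by this route, although Protocol 8.3.4 separately requires the Investigator to review every laboratory report.
- *Laboratory pause criteria (Protocol 8.4).* Both early-review criteria take the baseline grade as an input, so a meal-driven baseline grade can change which one a participant could meet. The Grade 3 criterion also needs a laboratory AE with no other explanation. The Grade 2 criterion also needs no other explanation and the Investigator's view that the finding is clinically meaningful. The study-wide criterion needs clinical significance and sits under a condition of relatedness agreed by Investigator and Sponsor.
- *Primary out-of-range endpoint.* It uses study-center ranges, not Table 10.4.

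**The case against.** The best reply is that these are drafting slips with little reach. The SAP grades only where a scale applies, and a fasting row can be read as not applying to a nonfasting sample. Diabetes and a body mass index of 30 or more are listed among the excluded conditions (Protocol 5.2, E13 and its footnote), which should limit high values. Most of the boundary faults affect a single value. Vaccination and scheduled safety sampling end early, and Protocol 9.5 records a partial database lock by Amendment 1, so hardly any dosing decision could still turn on this.

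Most of that stands as a limit on size. It does not remove the defect. The SAP phrase allows both readings and does not choose between them. Neither the exclusions nor the timing settles how a value is graded in the final tables.

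A reader might go further and infer that the pause counts are wrong. The documents do not support that, because no laboratory pause criterion counts raw grades. A meal is itself another explanation for a high glucose, and Protocol 10.3.1 treats an abnormal result as an AE only if the Investigator finds it clinically significant. The chance that two participants exceed 125 mg/dL is therefore not the chance of a pause.

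A reader might also infer that real differences between arms are hidden. That is not shown either. Arms are randomized and observer-blind, and meals affect samples in every arm. This adds noise to the grades, but no arm difference in glucose is identified or quantified.

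**Conclusion.** The plan is wrong as written on a narrow point. The fasting state of the glucose sample contradicts the only grading row for it. One value in Table 10.4 has two grades, three single values have none, and two platelet intervals have none if counts are not reported in whole thousands. Grades for these values are misapplied or undefined in the grade and shift tables and in the grade-triggered review. They may also affect inputs to the pause criteria.

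The effect has no single direction. A fasting scale on nonfasting glucose tends to over-grade, at baseline as well as afterwards, while the boundary gaps leave abnormal values without a grade. Its frequency cannot be sized from the documents, which give neither the distribution of nonfasting glucose nor the laboratories' reporting precision. Laboratory grades in general are not in doubt. The point is worth correcting before the final analysis, but it does not threaten the primary laboratory endpoint.

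**What to change.** - Reconcile Protocol Table 10.1, Protocol Table 10.4 and SAP 4.4.1.3 so that the glucose grading row matches the fasting state of the sample. The sponsor's medical team should choose the scale.
- Until that is done, report glucose only as within or outside the study-center normal range, and leave it out of the grade-by-visit and shift tables. The SAP does not say whether those ranges are fasting or nonfasting, so a footnote should.
- Make the Table 10.4 bands contiguous and non-overlapping at the precision the laboratories report, so that each value has exactly one grade. The cut-offs are for the sponsor to set.
- State which convention was used in any interim grade or shift tables already produced.

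The cost is an edit to one protocol table and one SAP sentence, plus a rerun of any affected tables. No new samples are needed.

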10.4 Appendix: Collection of Pregnancy Information

DEFINITIONS:

Woman of Childbearing Potential (WOCBP)

A woman is considered fertile following menarche and until becoming postmenopausal unless permanently sterile (see below).

If fertility is unclear (eg, amenorrhea in adolescents or athletes) and a menstrual cycle cannot be confirmed before first dose of study intervention, additional evaluation should be considered.

Women in the following categories are not considered WOCBP

- 1) Premenarchal
- 2) Premenopausal female with 1 of the following:
 - Documented hysterectomy
 - Documented bilateral salpingectomy
 - Documented bilateral oophorectomy

For individuals with permanent infertility due to an alternate medical cause other than the above, (eg, mullerian agenesis, androgen insensitivity), investigator discretion should be applied to determining study entry.

Note: Documentation can come from the site personnel's: review of the participant's medical records, medical examination, or medical history interview.

- 3) Postmenopausal female
 - A postmenopausal state is defined as no menses for 12 months without an alternative medical cause.
 - A high follicle stimulating hormone (FSH) level in the postmenopausal range may be used to confirm a postmenopausal state in women not using hormonal contraception or hormonal replacement therapy (HRT). However, in the absence of 12 months of amenorrhea, confirmation with more than one FSH measurement is required.
 - Females on HRT and whose menopausal status is in doubt will be required to use one of the non-estrogen hormonal highly effective contraception methods if they wish to continue their HRT during the study. Otherwise, they must discontinue HRT to allow confirmation of postmenopausal status before study enrollment.

COLLECTION OF PREGNANCY INFORMATION

The collection period of pregnancy information will correspond at least to the period during which the participant is requested to be under contraception. (according to protocol: effective method of contraception or abstinence from at least 4 weeks prior to the first vaccination until at least 12 weeks after the last vaccination). If there are any pregnancy during this period, follow-up should be conducted up to delivery: this will be covered by the 12-month surveillance of the study.

Female Participants who become pregnant

- The Investigator will collect pregnancy information on any female participant who becomes pregnant while participating in this study. The initial information together with the contraceptive method if any will be recorded on the appropriate form and submitted to the Sponsor within 1 month of learning of a participant's pregnancy.
- The participant will be followed to determine the outcome of the pregnancy. The Investigator will collect follow-up information on the participant and the neonate and the information will be forwarded to the Sponsor. Generally, follow-up will not be required for longer than 6 to 8 weeks beyond the estimated delivery date, but will be in accordance with local regulations. Any termination of pregnancy will be reported, regardless of fetal status (presence or absence of anomalies) or indication for the procedure.
- While pregnancy itself is not considered to be an AE or SAE, any pregnancy complication or elective termination of a pregnancy for medical reasons will be reported as an AE or SAE.
- A spontaneous abortion (occurring at < 22 weeks gestational age) or still birth (occurring at > 22 weeks gestational age) is always considered to be an SAE and will be reported as such.
- Any post-study pregnancy related SAE considered reasonably related to the study intervention by the Investigator will be reported to the Sponsor as described in [Section 8.3.4](#). While the Investigator is not obligated to actively seek this information in former study participants, he or she may learn of an SAE through spontaneous reporting.
- In case of pregnancy during the primary series and if at least 1 dose of the study vaccine(s) has been administered, the participant will not be discontinued from the study, but no further vaccination will be administered until after delivery (if applicable and still within the study vaccination window). However, the participant will be followed for safety assessment (and may be followed for immunogenicity assessment, if applicable).
- If primary series have been completed and the delivery occurs between the primary series and the booster, the booster dose can be administered. However, if vaccination is a contraindication for lactation (ie, live-attenuated vaccine), the participant may not be vaccinated with a booster dose.

10.5 Appendix: AESIs

Events potentially associated with coronavirus vaccine

Anaphylactic reactions

Generalized convulsion

Thrombocytopenia

Events potentially associated with AF03 adjuvant use

Dry eyes

Tearing

Dry mouth

Events potentially associated with the adjuvants use (AF03 or AS03) and/or coronavirus vaccine

NOCMCs:

NOCMCs are defined as any new ICD-10 diagnosis (10th revision of the International Statistical Classification of Diseases and Related Health Problems) that is applied to the participant during the course of the study, after receipt of the study agent, that is expected to continue for at least 3 months and requires continued health care intervention.

pIMDs:

Potential immune-mediated diseases (pIMDs) are a subset of AEs that include autoimmune diseases and other inflammatory and/or neurologic disorders of interest which may or may not have an autoimmune etiology. AEs that need to be recorded and reported as pIMDs include those listed in [Table 10.5](#).

However, the Investigator will exercise their medical and scientific judgment in deciding whether other diseases have an autoimmune origin (that is pathophysiology involving systemic or organ-specific pathogenic autoantibodies) and should also be recorded as a pIMD.

When there is enough evidence to make any of the diagnoses mentioned in [Table 10.5](#), the AE must be reported as a pIMD. Symptoms, signs or conditions which might (or might not) represent the above diagnoses, should be recorded and reported as AEs but not as pIMDs until the final or definitive diagnosis has been determined, and alternative diagnoses have been eliminated or shown to be less likely.

In order to facilitate the documentation of pIMDs in the eCRF, a pIMD standard questionnaire and a list of preferred terms (PTs) and PT codes corresponding to the above diagnoses will be available to investigators at study start.

Once a pIMD is diagnosed (serious or non-serious) in a study subject, the Investigator (or designate) must complete, date and sign an electronic Expedited Adverse Events Report.

Table 10.5: List of potential immune-mediated diseases

Neuroinflammatory disorders	Musculoskeletal disorders	Skin disorders

 • Cranial nerve neuropathy, including paralysis and paresis (eg, Bell's palsy). • Optic neuritis. • Multiple sclerosis. • Transverse myelitis. • Guillain-Barré syndrome*, including Miller Fisher syndrome and other variants. • Acute disseminated encephalomyelitis*, including site specific variants, eg, noninfectious encephalitis, encephalomyelitis, myelitis, myeloradiculoneuritis. • Myasthenia gravis, including Lambert-Eaton myasthenic syndrome. • Demyelinating peripheral neuropathies including: 
 - Chronic inflammatory demyelinating polyneuropathy. - Multifocal motor neuropathy. - Polyneuropathies associated with monoclonal gammopathy. • Narcolepsy*. 	
 • Systemic lupus erythematosus and associated conditions. • Systemic scleroderma (systemic sclerosis), including: 
 - Diffuse scleroderma. - CREST syndrome. - Idiopathic inflammatory myopathies, including: 
 - Dermatomyositis. - Polymyositis. - Anti-synthetase syndrome. - Rheumatoid arthritis and associated conditions including: 
 - Juvenile idiopathic arthritis. - Still's disease. - Polymyalgia rheumatica. - Spondyloarthropathies, including: 
 - Ankylosing spondylitis. - Reactive arthritis (Reiter's syndrome). - Undifferentiated spondyloarthritis. - Psoriatic arthritis. - Enteropathic arthritis. - Relapsing polychondritis. - Mixed connective tissue disorder. - Gout. 	
 • Psoriasis. • Vitiligo. • Erythema nodosum. • Autoimmune bullous skin diseases (including pemphigus, pemphigoid, and dermatitis herpetiformis). • Lichen planus. • Sweet's syndrome. • Localized scleroderma (morphea).
Vasculitis	Blood disorders	Others

 • Large vessels vasculitis* including: 
 - Giant cell arteritis (temporal arteritis). - Takayasu's arteritis. • Medium sized and/or small vessels vasculitis* including; 	
 • Autoimmune hemolytic anemia. • Autoimmune thrombocytopenia. • Antiphospholipid syndrome. • Pernicious anemia. • Autoimmune aplastic anemia. 	
 • Autoimmune glomerulonephritis including: 
 - IgA nephropathy. - Glomerulonephritis rapidly progressive. - Membranous glomerulonephritis.


 - Polyarteritis nodosa. - Kawasaki's disease. - Microscopic polyangiitis. - Wegener's granulomatosis (granulomatosis with polyangiitis). - Churg–Strauss syndrome (allergic granulomatous angiitis or eosinophilic granulomatosis with polyangiitis). - Buerger's disease (thromboangiitis obliterans). - Necrotizing vasculitis (cutaneous or systemic). - Antineutrophil cytoplasmic antibody (ANCA) positive vasculitis (type unspecified). - Henoch-Schonlein purpura (IgA vasculitis). - Behcet's syndrome. - Leukocytoclastic vasculitis. 	
 • Autoimmune neutropenia. • Autoimmune pancytopenia. 	
 - Membranoproliferative glomerulonephritis. - Mesangioproliferative glomerulonephritis. - Tubulointerstitial nephritis and uveitis syndrome. • Ocular autoimmune diseases including: • Autoimmune uveitis. • Autoimmune retinitis. • Autoimmune myocarditis. • Sarcoidosis. • Stevens-Johnson syndrome. • Sjögren's syndrome. • Alopecia areata. • Idiopathic pulmonary fibrosis. • Goodpasture syndrome. • Raynaud's phenomenon.
Liver disorders	Gastrointestinal disorders	Endocrine disorders

 • Autoimmune hepatitis. • Primary biliary cirrhosis. • Primary sclerosing cholangitis. • Autoimmune cholangitis. 	
 • Inflammatory bowel disease, including: 
 - Crohn's disease. - Ulcerative colitis. - Microscopic colitis. - Ulcerative proctitis. • Celiac disease. • Autoimmune pancreatitis. 	
 • Autoimmune thyroiditis (Hashimoto thyroiditis). • Grave's or Basedow's disease. • Diabetes mellitus type 1. • Addison's disease. • Polyglandular autoimmune syndrome. • Autoimmune hypophysitis.

* Events potentially associated with coronavirus vaccine

